#### **9.7.4 Laboratory parameters**

Blood samples will be collected as given in [Table 9–1](#) and the following biomarkers will be determined in plasma/serum by a central laboratory using validated assays platforms including appropriate quality controls:

- NTproBNP
- hs-Copeptin
- hs-TNT

Further biomarkers may be tested:

- GDF15
- IGFBP7
- sST2
- Gal3

Details on the collection, processing, storage and shipment of biomarker samples will be provided in separate documents (e.g. sample handling sheets or lab manual). In addition to the biomarkers listed above, other biomarkers deemed relevant to gain further knowledge about the pathomechanisms of the disease may be measured, based on newly emerging data from other ongoing studies and / or literature data.

#### **9.8 Appropriateness of procedures / measurements**

All laboratory and safety parameters as well as the methods to measure them, are standard variables/ methods in clinical studies and/ or clinical practice. They are widely used and generally recognized as reliable, accurate and relevant.

## **10. Statistical methods and determination of sample size**

### **10.1 General considerations - amended**

All statistical details including calculated variables and proposed format and content of tables will be detailed in the Statistical Analysis Plan (SAP). The SAP will be finalized before study database lock. Statistical analysis will be performed using SAS or R; the versions used for both types of software will be specified in the SAP.

Statistical analyses will be of explorative and descriptive nature. The study is not aimed to confirm or reject pre-defined hypotheses; however, particular attention will be given to the ejection fraction (preserved versus reduced) as stratification factor.

All variables will be summarized with appropriate statistical methods: categorical variables by frequency tables (absolute and relative frequencies) and continuous variables by sample statistics (i.e. mean, standard deviation, minimum, median, quartiles and maximum).

Continuous variables will be described by absolute value and as change from baseline per analysis time point, as applicable.

Data from VitalPatch and DynaPort devices is expected to include missing values, as result of compliance in wearing the device. The amount of missing data within a day cannot be predicted and will be an outcome of the study. Missing data within day will be assessed by vendors according their validated algorithms of data pre-processing and quality check. No imputation will be performed in case day monitoring did not pass quality checks. The amount of missing monitoring will be assessed prior each statistical analysis and in presence of outliers the exclusion of subjects' data may occur.

All analyses will be performed for the FAS population (overall analysis) and separately for each participating country if subject numbers are sufficient and if required for local reasons.

Sample size and disposition information by analysis time point will be displayed in a frequency table.

All therapies documented will be coded using the World Health Organization – Drug Dictionary. Medical history, any diseases and AEs will be coded using the latest Medical Dictionary for Regulatory Activities (MedDRA) version.

No interim analyses are planned. The final analysis will be performed after end of the study which is the date the analytical dataset is completely available.

### **10.2 Analysis sets - amended**

In absence of intervention and randomization the statistical analysis sets are defined on the base of a successful monitoring under the VitalPatch biosensor patch.

#### **Full analysis set (FAS)**

The FAS population consists of all subjects that are included into the study and that are wearing at least one VitalPatch biosensor patch and for which data was successfully collected over the whole week. The FAS will be used to display baseline characteristics, assess parameter variability, correlative analyses.

---

 Replacement of AVIVO MPM with VitalPatch Biosensor as per Amendment 2 (Section 15.2)

## **Safety analysis set (SAF)**

The SAF population consists of all patients with a planned study procedure after signing the informed consent that are wearing at least one VitalPatch biosensor patch and for which data was successfully collected over the whole week will be included in the SAF. The SAF will be used to display safety analyses.

### **10.3 Variables and planned statistical analyses**

Given the descriptive nature of the study and the multivariate nature of the statistical approach used, all of the variables mentioned in section 9 are suitable to be analyzed.

In addition, variables including patient heart failure information (preserved vs reduced ejection fraction) or other clinical endpoints (e.g. re-hospitalization for heart failure, cardiovascular death, emergency visits) will be considered as well in the statistical analysis, possibly in interaction with other relevant parameters.

#### **10.3.1 Analysis of demography, disease details, prior and concomitant medication and other baseline data**

Summary statistics (arithmetic mean, standard deviation, median, minimum and maximum for quantitative variables) will be presented for total and study part. Frequency tables for qualitative data will be provided.

Unsupervised patient stratification at baseline will be carried out by means of the following multivariate techniques which allow the simultaneous analysis of many variables such as from demographics, disease history (MedDRA terms), co-morbidities, prior and concomitant medication, AEs, NYHA classification, ECG judgement, vital signs, KCCQ/PRO scores, and biomarkers (laboratory data). Continuous variables will be arbitrary discretized in tertiles or quartiles according their density distribution or according existing clinical ranges of normality. Multiple correspondence analyses will be used, subjects will be displayed in bi-dimensional maps and the homogeneity of the population towards all the variables under assessment will be observed. If groups of subjects with specific co-occurrences for one or more parameters could be separated by the others in the bi-dimensional map (at 95% confidence ellipse) those will be flagged and eventually considered as separate population for the analysis. In the latter case, the parameter(s) responsible for the separation will be identified using the map of contribution of variable categories to the dimensions, and could be used as covariate in modeling. No additional investigations for comparative purposes will be performed.

#### **10.3.2 Analysis of data within the hospitalization phase - amended**

Data collected in the hospitalization phase for which records will be available until visit 1 (from hospitalization and at hospital discharge, respectively) will be analyzed by means of multivariate techniques in order to describe changes and quantify the variability of changes in this early phase, and eventually identify subjects with extreme behavior in one or more of the parameters under measurement. Changes in the parameters from 12-lead ECG, vital signs, KCCQ/PRO scores, and biomarkers will be described using multilevel Partial Least Square analysis. Such model allows conducting a paired analysis of subjects before and after hospitalization, hence to observe a potential effect of hospitalization on the observed parameters. If an effect will be observed, the parameters sensitive to hospitalization will be

assessed using linear mixed model as described in Section 10.3.3.1 but within the hospitalization time frame.

For VitalPatch data collected in this frame only the day to day variability will be of interest.

### 10.3.3 Analysis of primary and secondary outcomes

#### 10.3.3.1 Assessment of variability

The variability between subjects and within subjects across time for each of the parameters of interest will be described using a linear mixed model (LMM) with subject as random factor, and time as fixed factor, possibly including additional covariates as may result from the assessment at baseline for patient stratification or as required for clinical interpretation.

In addition to effects and interactions of fixed effects parameters LMMs will be used to estimate simultaneously parameters of the variance and covariance components of random effects due to subjects.

The LMM for the parameter of interest (Y) as selected among the molecular and digital biomarkers available (i.e. laboratory parameters and device generated digital data) will have the following base annotation:

$$Y_{st} = \beta_0 + \beta_1 \cdot TIME_t + S_{0s} + \varepsilon_{st}$$

Where S is subject (random) and TIME represents visit, with baseline as reference.

The HF type (preserved/reduced) will be included in the model (here denoted as C), as random factor, and the effect on intercept or slope will be assessed:

$$Y_{st} = \beta_0 + (\beta_1 + C_{1s}) \cdot TIME_t + S_{0s} + C_{0s} + \varepsilon_{st}$$

Where  $C_{1s}$  will be the effect of HF type on the slope (e.g., if changes in physical activity are different between the two sub-populations) and  $C_{0s}$  will be the effect on the intercept (e.g., if the two sub-populations have different baseline values).

Given the high number of parameters involved and the exploratory nature of the study, all of the possible models will not be addressed here, and the base model will be extended as appropriate depending on the specific question to address and the given subset of parameters involved.

Testing of random effects and visualization of residuals will be performed in order to highlight single subjects (or sub-group) showing outstanding or peculiar characteristics.

Estimates from the model will be used to quantify the ability of a parameter to measure clinically relevant changes over time. The intraclass correlation coefficient (ICC) will be used as key statistic when considering the relative proportion of within- and between-individual variation is the expected correlation among measurements from the same individual, it can indicate the degree of difference between individuals and will also be used as measure reliability (ability to reflect true between-individual differences). For any sample, the ICC will be calculated with estimates from LMMs of both between-individual variance and within-individual variance, according the following:

$$ICC = \tau^2 / (\tau^2 + \sigma^2)$$

---

 Replacement of AVIVO MPM with VitalPatch Biosensor as per Amendment 2 (Section 15.2)

where  $\tau^2$  is a commonly used symbol for between-individual variance (variance of  $S_{0s}$  term in in the base model above) and  $\sigma^2$  for within-individual variance (variance of  $\varepsilon_{st}$  in the base model). Then, ICC will be the proportion of total variance ( $\tau^2 + \sigma^2$ ) attributable to between-individual differences ( $\tau^2$ ).

In addition, point estimates (LS-Means) and exploratory 90% confidence intervals will be calculated for comparing baseline and 3 months data by HF type (preserved/reduced), and may include intermediate time points if available.

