## 10.4 Determination of sample size

Due to the exploratory nature of this study, the number and the diversity of parameters used to measure physical activity, or which could affect this outcome in “real-life” conditions, no modeling for power estimation was performed. The number of subjects was set to be comparable to other studies which involved the assessment of physical activity on daily life (activity monitoring) and where a significant difference in PA was observed (60 subject in

---

 Replacement of AVIVO MPM with VitalPatch Biosensor as per Amendment 2 (Section 15.2)

average). Also considering the expected variability due to measurement under unstandardized conditions [12] a number of 80 subjects (HFpEF n=60, HFrEF n=20) who completed the main study (i.e. visit 4) was defined as target.

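### Protocol 10.3.3.1 treats HF type, a two-level design factor, as random, so the model as written cannot give the LS-means by HF type that it promises and shrinks the HFpEF–HFrEF contrast

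*Protocol*

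**What the plan says.** Protocol 10.1 calls the analysis exploratory but adds that "particular attention will be given to the ejection fraction (preserved versus reduced) as stratification factor". Protocol 10.3.3.1 then sets out a linear mixed model for any parameter "as selected among the molecular and digital biomarkers available (i.e. laboratory parameters and device generated digital data". The base model has a fixed intercept, fixed time and a random subject intercept. The extension adds HF type: "The HF type (preserved/reduced) will be included in the model (here denoted as C), as random factor". Its slope term is meant to show "if changes in physical activity are different between the two sub-populations", and its intercept term "if the two sub-populations have different baseline values". The section closes with the output: "point estimates (LS-Means) and exploratory 90% confidence intervals will be calculated for comparing baseline and 3 months data by HF type (preserved/reduced").

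On size, Protocol 10.4 says that "a number of 80 subjects (HFpEF n=60, HFrEF n=20) who completed the main study (i.e. visit 4) was defined as target", and that "no modeling for power estimation was performed".

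The SAP (version 1.0) differs. Its two mixed models, in 6.5.2.2 (diary Overall Activity Score) and 6.5.4.1 (DynaPort), contain subject, visit and the baseline value, with no HF-type term. SAP 6.5.3 summarises laboratory biomarkers descriptively by cohort and visit. SAP 4.1 leaves patch data to the biomarker analyses and gives no model for them. SAP 2 reports a low number of subjects because recruitment stopped early, without giving the number. SAP 7.2 says the protocol's analyses were comprehensively revised. It does not mention the LS-means by HF type or this model term.

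**The concern.** A random factor suits levels that are a sample from a wider population of levels. HFpEF and HFrEF are not such a sample. They are the two groups defined by inclusion criteria 5 and 6, enrolled to separate targets, and the protocol asks how these two groups differ.

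Two consequences follow. First, LS-means are functions of the fixed effects, and the fixed part of the formula is the same for both HF types. Second, what the model does give for each type is a prediction shrunk towards the common mean, with a variance estimated from a single contrast between two levels. If that estimate is zero, the predicted difference is exactly zero.

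At stake is the comparison singled out in Protocol 10.1. Protocol 6.3 uses the HFrEF patients as an internal plausibility control, and pulling the two groups together weakens that check.

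**Working it through.** **Inputs from the documents.** HF type is random on intercept and slope, and the promised intervals are at 90% (Protocol 10.3.3.1). The target is 60 HFpEF and 20 HFrEF (Protocol 10.4). No figure for this contrast is stated, so there is nothing to reproduce.

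**Assumptions.** The true HFpEF–HFrEF difference *d* is taken from 0 to 1 SD, with the SD set to 1. Since recruitment stopped early, splits of 30/10 and 20/7 are used as sensitivity cases. C is read as an effect of HF type. The formula indexes C by subject; taken literally, the intercept part of C could not be separated from the subject intercept, and the model would estimate no HF-type difference at all.

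**Step 1: are there LS-means by HF type?** The fixed part is β0 + β1·TIME for HFpEF and β0 + β1·TIME for HFrEF. These are identical, so LS-means from this model cannot differ by HF type, whatever the effect size.

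**Step 2: what the random term does.** Let D be the observed difference in group means, s² the residual variance, and h = n1·n2/(n1+n2). At 60/20, h = 1200/80 = 15. At 30/10, h = 300/40 = 7.5. At 20/7, h = 140/27 = 5.19. With F = h·D²/s²:

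- REML estimate of the HF-type variance = max{0, (D² − s²/h)/2}, which is zero exactly when F < 1.
- Predicted difference = D·max(0, 1 − 1/F).

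The chance of a zero estimate is P(F < 1) for a noncentral F with 1 and n1+n2−2 degrees of freedom and noncentrality h·d². Mean predicted differences come from 400,000 draws.

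| Split | d (SD) | h·d² | Variance set to 0 | Mean predicted difference | Share retained |
|---|---|---|---|---|---|
| 60/20 | 0 | 0 | 68% | 0 | n/a |
| 60/20 | 0.2 | 0.60 | 55% | 0.109 | 55% |
| 60/20 | 0.3 | 1.35 | 42% | 0.183 | 61% |
| 60/20 | 0.5 | 3.75 | 17% | 0.372 | 74% |
| 60/20 | 0.8 | 9.60 | 2% | 0.708 | 88% |
| 60/20 | 1.0 | 15.0 | 0.2% | 0.928 | 93% |
| 30/10 (assumed) | 0.5 | 1.88 | 35% | 0.322 | 64% |
| 20/7 (assumed) | 0.5 | 1.30 | 42% | 0.304 | 61% |

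Hand check at 60/20, d = 0.5, by normal approximation: √15 × 0.5 = 1.94, and P(|Z + 1.94| < 1) = Φ(−0.94) − Φ(−2.94) ≈ 0.17.

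**Step 3: direct fits.** In 300 simulated data sets per case at 60/20, REML gave a zero variance in 68% (d = 0) and 17% (d = 0.5), matching the formula. Maximum likelihood gave 89% and 38%.

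**Step 4: intercept and slope together.** In the two-visit model at 60/20 (assumed within-subject correlation 0.7, 500 runs per case), the slope variance was zero in 64–72% of runs with no true slope difference, 41–44% at 0.2 SD and 26–27% at 0.3 SD.

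**Step 5: fixed effect.** The estimated difference is unbiased at every *d*. The 90% interval has half-width t(0.95; 78)/√15 = 0.43 SD at 60/20, and 0.62 SD at 30/10.

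**The case against.** The strongest case against the point concerns its reach. The SAP revises the protocol's analyses. Its mixed models carry no HF-type term, and laboratory markers, vital signs and DynaPort values are shown by cohort as plain means and SDs, which do not shrink. A reader might infer that the DynaPort, diary or laboratory results will be distorted by this error; the SAP does not support that. It is also not stated that the protocol formula will be used for the patch data, only that the SAP offers no other model for them. This part of the objection stands and limits the point.

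A second argument is that the promised LS-means compare baseline with 3 months within each HF type, and that fitting the base model separately by type would supply them. The protocol also allows the base model to be extended as needed. So it would be too strong to say that the LS-means are unobtainable. They are unobtainable from the model as written, and separate fits would not by themselves estimate the between-type differences that the two C terms are meant to assess.

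A third argument is about size. A reader might infer that the model usually sets the contrast to zero. The documents give no effect size, and at 60/20 a zero is rare for a difference of 0.8 SD or more. Shrinkage, by contrast, applies at every size of difference.

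Finally, the section's key statistic, the ICC, is defined from the subject and residual variances of the base model, which contains no C. It is not affected.

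**Conclusion.** The point holds for the text of Protocol 10.3.3.1. The random-factor specification and the promise of LS-means by HF type do not fit together, and this needs no assumption about effect size. The amount of shrinkage does depend on assumptions: REML, C read as an HF-type effect, and the chosen differences and splits. At 60/20 the loss is substantial for differences of 0.2 to 0.5 SD and small by 1 SD. It grows with a smaller sample or with maximum likelihood.

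The practical reach is the protocol text, any patch analysis that takes its model from this section, and any later model that brings HF type back. No hypothesis is tested for confirmation, so the severity is minor to moderate.

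**What to change.** In Protocol 10.3.3.1, and in any patch or biomarker model that includes HF type, replace the C terms with fixed effects:

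Y_st = β0 + β1·TIME_t + β2·HF_s + β3·HF_s·TIME_t + S_0s + ε_st,

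with TIME as visit (categorical, baseline as reference), HF_s the HF type of subject *s*, and subject the only random factor. Take the LS-means and 90% intervals by HF type and visit from this model. β2 is then the baseline difference and β3 the difference in change. Keep the ICC from the base model, as now defined.

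The biomarker analysis plan for the patch data should state this model. If LS-means by HF type are no longer intended, SAP 7.2 should say so.

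The cost is one line in the model statement. No extra data or patients are needed.
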